3.7.4 Secondary Analysis of LDL-C

The following treatment targets will be explored:

- Reaching LDL-C at Week 12 LOCF <100 mg/dL. Patients who have cardiovascular disease will be excluded from this analysis.
- Reaching LDL-C at Week 12 LOCF <70 mg/dL.
- Reaching LDL-C target endpoint at Week 12: For patients who have cardiovascular disease, the target endpoint is <70 mg/dL; and for all other patients the target endpoint is <100 mg/dL.

For the analysis reaching LDL-C <100 mg/dL, <70 mg/dL, or the target endpoint at Week 12 LOCF, a logistic regression model with treatment as a factor and baseline LDL-C as a covariate will be used. The odds ratio, confidence intervals and p-values from the logistic regression analysis will be presented for the treatment difference between MGL-3196 and placebo.

Sample SAS® code for logistic regression is provided below:

```
*****

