4 SELECTION AND WITHDRAWAL OF PATIENTS

4.1 Inclusion Criteria

The population for this study is male and female patients ≥ 18 years of age who have met the diagnostic criteria for HeFH outlined by the Simon Broome Register Group (Appendix C) World Health Organization (WHO)/Dutch Lipid Network (score >8 ; Appendix D).

Patients who meet all of the following criteria will be eligible to participate in the study:

1. Must be willing to participate in the study and provide written informed consent;
2. Male and female adults ≥ 18 years of age;
3. Female patients of child bearing potential with negative serum pregnancy (beta human chorionic gonadotropin) test who are not breastfeeding, do not plan to become pregnant during the study, and agree to use effective birth control (ie, condoms, diaphragm, non-hormonal intrauterine device [IUD], or sexual abstinence [only if this is in line with the patient's current lifestyle]) throughout the study and for at least 1 month after study completion; hormonal contraception (estrogens stable ≥ 3 months) and hormonal IUDs are permitted if used with a secondary birth control measure (eg, condoms); OR female patients of non-child bearing potential (ie, surgically [bilateral oophorectomy, hysterectomy, or tubal ligation] or naturally sterile [>12 consecutive months without menses]); male patients who have sexual intercourse with a female partner of child bearing potential from the first dose of study drug until 1 month after study completion must either be surgically sterile (confirmed by documented azoospermia >90 days after the procedure) OR agree to use a condom with spermicide. All male patients must agree not to donate sperm from the first dose of study drug until 1 month after study completion;
4. Must have a diagnosis of HeFH by genetic testing or by having met the diagnostic criteria for definite familial hypercholesterolemia outlined by the Simon Broome Register Group (Appendix C) or WHO/Dutch Lipid Network (score >8 ; Appendix D);
5. Must have a fasting LDL-C ≥ 2.6 mmol/L (100 mg/dL); and
6. Must be on a stable or maximally tolerated dose (≥ 4 weeks prior to screening) of an approved statin (rosuvastatin ≤ 20 mg daily, atorvastatin ≤ 80 mg daily), with or without ezetimibe.

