10.2.1.2 Secondary efficacy analysis

For the continuous secondary efficacy variables, the same ANCOVA model will be used. Normality will be tested for the model residuals. For certain efficacy variables, logarithm transformation may be performed prior to fitting the ANCOVA model. For the categorical secondary efficacy variables, Fisher's exact test will be used to compare the odds ratio between MGL-3196 doses versus placebo.

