** ANL01FL = Reaching treatment goal, where 1=Yes 0=No          **
** TRT = Treatment group where 0 = placebo, 1= MGL-3196          **
** BASE = Baseline LDL-C                                         **
*****
PROC GENMOD DESCENDING;
  CLASS TRT;
  MODEL ANL01FL = TRT BASE / d=b link=logit;
  ESTIMATE "MGL3196 vs Placebo" TRT -1 1;
RUN;
```

It is observed that the screening values and baseline values of LDL-C have relatively high variation. Therefore, the change from screening to Week 12 LOCF in LDL-C will also be explored.

Due to the variation between screening and baseline values of LDL-C, it is expected that some patients will have baseline LDL-C <100 mg/dL. Therefore, more exploratory analysis of reaching LDL-C treatment goals at Week 12 based on patients with baseline LDL-C ≥100 mg/dL only may be conducted.

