4. SAMPLE SIZE DETERMINATION

Up to 105 patients in total will be randomized to 1 of 2 treatments (70 patients to MGL-3196, 35 patients to placebo). It is estimated that the treatment difference of percent change in LDL-C from baseline to Week 12 between any dose of MGL-3196 group and the placebo group is about -20%. With a common standard deviation for the change in LDL-C at 20%, 27

patients per group to complete the Week 12 visit will provide 90% power with a two-sample t-test. The significance level is set as 0.025 for the consideration of multiplicity in comparisons of 2 daily dosing regimens of MGL-3196 vs. placebo group. The enrollment size is designed to allow for dropouts before the 12-week visit, and as such, patients who drop out of the study will not be replaced.

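### The exploratory LDL-C <70 mg/dL goal is analysed by ordinary maximum-likelihood logistic regression, which gives no usable odds ratio or p-value if no placebo patient reaches goal, and the SAP has no rule for that case

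*SAP*

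**What the plan says.** SAP 3.7.4 introduces three Week 12 goals with the words "The following treatment targets will be explored". One is "Reaching LDL-C at Week 12 LOCF <70 mg/dL"; the others are <100 mg/dL (leaving out patients with cardiovascular disease) and a composite whose cut-off depends on cardiovascular disease. For all three, "a logistic regression model with treatment as a factor and baseline LDL-C as a covariate will be used". The same section adds: "The odds ratio, confidence intervals and p-values from the logistic regression analysis will be presented".

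The sample code is PROC GENMOD with "MODEL ANL01FL = TRT BASE / d=b link=logit" and an ESTIMATE contrast for treatment. It requests no penalised, exact or likelihood-ratio output, and no text covers an empty cell or non-convergence. The section also allows a repeat analysis restricted to patients with baseline LDL-C of at least 100 mg/dL.

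For categorical secondary variables in general, Protocol 10.2.1.2 says Fisher's "exact test will be used to compare the odds ratio between MGL-3196 doses versus placebo". SAP 3.7.5 keeps Fisher's test for categorical variables.

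**The concern.** Inclusion criterion 5 (Protocol 4.1) requires a fasting LDL-C of at least 100 mg/dL, and inclusion criterion 6 requires background statin. A placebo patient whose baseline is still 100 mg/dL or more needs a fall of at least 30% to be below 70. The placebo arm is small ("70 patients to MGL-3196, 35 patients to placebo"), so it could easily have no patient at goal.

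Maximum-likelihood logistic regression then breaks down. The fitted odds ratio has no finite value and its standard error grows without limit, so a Wald test cannot reject however many drug patients reach goal. The report would carry an odds ratio, interval and p-value that mean nothing, in a pattern that an effective drug can produce. Any replacement would be chosen after the empty cell had been seen.

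**Working it through.** **Inputs from the documents.** Difference of -20 percentage points and SD 20% (Protocol 10.2.4, SAP 4); 70 drug and 35 placebo patients (SAP 4); entry LDL-C at least 100 mg/dL (Protocol 4.1). SAP 3.7.4 also says that screening and baseline values vary a good deal and that some baselines will be under 100. As a check on these inputs, the noncentral t distribution at two-sided 0.025 gives power 0.898 with 26 per group and 0.910 with 27, which reproduces the plan's 27 per group for 90%.

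**Inputs assumed.** The baseline LDL-C distribution, the visit-to-visit noise, and no mean change on placebo. The documents give none of these.

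**Step 1: the mechanism.** Let logit P(goal) = α + β·TRT + γ·BASE. With no placebo responder, lower α and raise β so that α + β stays fixed. The drug patients' likelihood does not change, and each placebo term log(1 - p) rises towards 0. The likelihood therefore keeps increasing as β goes to infinity, whatever γ is.

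Example without the covariate, 8/70 v 0/35, Newton steps from zero:
- after 10 steps, log odds ratio 9.2, SE 45.8, z = 9.2/45.8 = 0.20, p = 0.84;
- after 25 steps, log odds ratio 24.2, SE about 82,800, p > 0.999.

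The printed p-value depends on when the algorithm stops. SAS itself was not run. That the reported test is Wald is inferred from the ESTIMATE statement and the absence of any likelihood-ratio request.

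**Step 2: chance of an empty placebo cell at a single baseline B.** P(<70) = Φ((100·(70/B - 1))/20) and P(none of 35) = (1 - p)^35.

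| B (mg/dL) | change needed | p | P(none of 35) |
|---|---|---|---|
| 100 | -30.0% | 6.7% | 9% |
| 120 | -41.7% | 1.9% | 52% |
| 130 | -46.2% | 1.05% | 69% |
| 150 | -53.3% | 0.4% | 87% |

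**Step 3: over a distribution of baselines.** Log-normal true LDL-C with mean 120, 135 or 150 and SD 35, eligibility at screening of 100 or more, and noise at both screening and baseline. Mean baseline after selection is about 135-155 mg/dL. P(no placebo responder) is:
- 10% noise: about 39-66%;
- 15% noise: 24-52%;
- 20% noise: 11-36%;
- 25% noise: 4-20%.

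A wider set of baselines (means 128-188) with log-scale noise of 0.08 or 0.15 gave 19-78%, and 52-89% in the restriction to baseline of at least 100.

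**Step 4: what the test does.** In simulated trials from that wider set with no placebo responder and at least one drug responder, the Wald test rejected in 0% (median p 0.996-0.998). The likelihood-ratio test on the same data rejected in 31-100%. Over all trials at the plan's effect and two-sided 0.05, power was 0.2-31% for maximum likelihood with Wald and 1-43% for Fisher. For Firth with a penalised likelihood-ratio test it was 18-60%, on a narrower set of baselines, with null rejection of 0.4-3.2%.

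**Step 5: realistic counts.** At 10% noise about 5.6-9.4 drug patients are expected at goal. Against 0/35:

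| drug at goal | Fisher p | Firth p, unadjusted |
|---|---|---|
| 6/70 | 0.175 | 0.085 |
| 7/70 | 0.092 | 0.054 |
| 8/70 | 0.050 | 0.034 |

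For a 2×2 table the Firth odds ratio adds one half to each cell. For 8/70 it is (8.5 × 35.5)/(62.5 × 0.5) = 9.7, which is finite.

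**Step 6: the <100 mg/dL goal.** Under the 10% noise model, P(no placebo patient <100) with all 35 patients is at most about 1.7%. Leaving out patients with cardiovascular disease raises this by an unknown amount. The composite goal was not computed.

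**The case against.** The strongest reply has four parts.

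- **Fisher is still in the SAP.** A reader might infer that the SAP dropped the protocol's exact test. It did not: SAP 3.7.5 keeps it for categorical variables. But 3.7.4 assigns these goals to the logistic model and does not link them to 3.7.5, and Fisher's test ignores baseline. The gap is an unstated fallback, not a deleted method.
- **How often it happens is assumed.** A reader might infer that an empty placebo cell is the usual outcome. The documents do not support that. They give no baseline distribution, and their remark on high screening-to-baseline variation favours the noisier scenarios, where the chance falls to 11-36% or lower. If visit noise also drives the Week 12 value, so that low baselines drift back up, the chance rises to 84-97%.
- **The loss is easily exaggerated.** With 12/70 v 0/35, Fisher gives p = 0.008 while the maximum-likelihood p lies between about 0.75 and above 0.999. But 12 exceeds the 5.6-9.4 expected at 10% noise. At 6 or 7 drug responders the valid tests are not significant at 0.05 either, and in the drift-back scenario Firth power was only 0-8.4%.
- **The stakes are low.** Goal attainment is not among the stated secondary objectives, the targets are exploratory, and the code is labelled as a sample.

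These parts limit the frequency, scope and severity of the point. They do not touch the mechanism, or the SAP's commitment to present estimates from a model that may not have any.

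**Conclusion.** The point holds as a minor one, for the <70 mg/dL goal. If no placebo patient and at least one drug patient reaches goal, the planned odds ratio is infinite and the planned p-value carries no information; this follows from the likelihood and needs no assumption about baseline. The chance of an empty placebo cell is roughly 10-66%. That rests on the plan's SD of 20%, 35 placebo patients, no mean placebo change, assumed mean baselines of about 135-155 mg/dL and visit noise of 10-20%.

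The separation risk is not shown for the <100 or composite goals, so a reader should not extend it to all of 3.7.4. The primary LDL-C analysis does not use this model and is unaffected.

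**What to change.** In SAP 3.7.4, for the <70 mg/dL goal and its optional repeat in patients with baseline of at least 100 mg/dL, replace the GENMOD code with Firth penalised logistic regression, keeping TRT and BASE (PROC LOGISTIC with FIRTH, CLPARM=PL and CLODDS=PL). Report the profile-likelihood interval and the penalised likelihood-ratio p-value, with the treatment coefficient set to zero within the full model so that test and interval agree. Present the number at goal in each arm beside the model result. Using the same model for the <100 and composite goals is optional, for consistency.

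The cost is a few lines of text and code and no new data. The downside is slight shrinkage of the odds ratio. With an empty cell the upper limit will still be very wide. The change gives an interpretable estimate and a valid test; it does not create power that 35 placebo patients cannot supply.

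### The own-target LDL-C goal is modelled without the factor that sets each patient's target: a valid analysis, but one that gives up a little power and clarity for nothing

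*SAP*

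**What the plan says.** SAP 3.7.4 introduces the goals with "The following treatment targets will be explored". There are three:

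- LDL-C below 100 mg/dL, where "Patients who have cardiovascular disease will be excluded from this analysis".
- LDL-C below 70 mg/dL, one limit for everyone.
- An own-target goal: "For patients who have cardiovascular disease, the target endpoint is <70 mg/dL; and for all other patients the target endpoint is <100 mg/dL".

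One model serves all three: "a logistic regression model with treatment as a factor and baseline LDL-C as a covariate will be used". The sample code in the same section agrees: "MODEL ANL01FL = TRT BASE / d=b link=logit". It has no CVD term, target term or distance-to-target covariate. An odds ratio, confidence intervals and p-values are to be reported.

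Goal attainment is not in the visible list of secondary efficacy variables in SAP 2.3.1 (the exploratory list there is redacted). SAP 3.7.5 makes no multiplicity adjustment for secondary and exploratory endpoints. SAP 4 plans power only for percent change in LDL-C. Protocol 5.3 names no stratification factor for the 2:1 randomisation.

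**The concern.** Baseline LDL-C is in the model because it says how far a patient must fall to reach the goal. That works when everyone analysed shares one limit, as in the first two goals. In the third goal the limit depends on CVD status, so two patients with the same baseline can face very different tasks, and the model treats them as alike.

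At stake are some power and the meaning of the reported odds ratio, which averages over two groups with different chances of success. The information that would separate them has already been collected and derived.

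**Working it through.** **1. The plan's own figure.** SAP 4 takes the difference in percent change "between any dose of MGL-3196 group and the placebo group is about -20" per cent and states "With a common standard deviation for the change in LDL-C at 20" per cent. It adds: "The significance level is set as 0.025 for the consideration of multiplicity". With a two-sided 0.025 level and 90% power, n per group = 2(z0.9875 + z0.90)² × (SD/difference)² = 2(2.241 + 1.282)² × (20/20)² = 24.8, so 25. The exact noncentral-t calculation gives 89.8% power at 26 and 91.0% at 27. The stated 27 per group is reproduced. It concerns percent change only; no power is stated for the goals.

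**2. Distance to goal at a baseline of 120 mg/dL.** The required change is 100/120 - 1 = -16.7% without CVD and 70/120 - 1 = -41.7% with CVD. Let percent change be normal with SD 20 and mean -20 on drug or 0 on placebo:

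- Without CVD: drug Φ((-16.7 + 20)/20) = 57%; placebo Φ(-16.7/20) = 20%.
- With CVD: drug Φ((-41.7 + 20)/20) = 14%; placebo Φ(-41.7/20) = 2%.

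The treatment-plus-baseline model gives these two kinds of patient the same fitted probability within an arm.

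**3. Size, by simulation.** The inputs from SAP 4 are the -20 effect, SD 20 and 70 versus 35 patients. The rest is assumed because the documents do not give it: baseline mean/SD, CVD share, CVD independent of baseline, and a two-sided 0.05 level (SAP 3.7.4 states none). Week 12 LDL-C is baseline × (1 + percent change). Both models were fitted to the same 1,000 trials per row. Odds ratios come from 300,000 simulated patients. Each cell shows treatment + baseline, then the same model with CVD added.

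| Baseline mean/SD | CVD share | Odds ratio | Likelihood-ratio power, % | Wald power, % |
|---|---|---|---|---|
| 120/30 | 10% | 4.56, 5.12 | 85.6, 88.0 | 84.5, 86.9 |
| 140/40 | 10% | 4.67, 5.12 | 81.3, 84.5 | 78.6, 82.0 |
| 160/50 | 10% | 4.79, 5.13 | 72.5, 73.9 | 67.4, 68.2 |
| 120/30 | 25% | 4.01, 5.14 | 82.8, 88.1 | 81.3, 86.5 |
| 140/40 | 25% | 4.22, 5.09 | 73.6, 78.5 | 69.6, 75.8 |
| 160/50 | 25% | 4.42, 5.11 | 65.9, 70.2 | 57.6, 61.6 |
| 120/30 | 50% | 3.78, 5.28 | 73.8, 82.8 | 70.8, 79.8 |
| 140/40 | 50% | 3.92, 5.15 | 68.4, 76.6 | 58.8, 68.6 |
| 160/50 | 50% | 4.08, 5.16 | 57.3, 63.5 | 42.4, 49.4 |

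Likelihood-ratio gains are about 1-3 points at a 10% share, 4-5 at 25% and 6-9 at 50%. The odds ratio rises by between 5.13/4.79 - 1 = 7% and 5.28/3.78 - 1 = 40%. Simulation error is about 1.5 points per power figure; differences are tighter because both models use the same trials.

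**4. A second baseline assumption.** Here patients are screened at 100 mg/dL or above, with a 10% within-person coefficient of variation and 1,500 trials per setting. Wald power for treatment + baseline versus log(baseline/own target) was:

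- Mean/SD 140/35, CVD 20%: 67% to 71%; median odds ratio 5.2 to 6.3.
- 140/35, CVD 35%: 57% to 63%; 5.0 to 6.5.
- 130/30, CVD 50%: 55% to 62%; 4.6 to 6.2.

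The log-ratio covariate did as well as a CVD factor.

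**5. Sensitivity (140/40, likelihood-ratio power).**

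- CVD patients 15-30 mg/dL lower at baseline, share 25-50%: gain 5-6 points.
- Effect of -12 instead of -20, share 10-50%: gain 2-6 points.
- 54 versus 27 completers, share 25%: 61.6% to 68.4%.

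**6. Under no effect (140/40, CVD 25%).** Rejection rates are 5.3% and 5.1% (likelihood ratio) and 3.5% for each model (Wald). Both models hold their level.

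**The case against.** **The analysis is exploratory and unpowered.** No confirmatory conclusion rests on this p-value, and the primary result is untouched. This stands, and it sets the severity.

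**The larger odds ratio does not correct a bias.** A reader might infer that leaving out the target biases the treatment effect towards no effect. The documents do not support that. The shift is non-collapsibility: treatment + baseline estimates a valid odds ratio averaged over the two target groups, and adding CVD estimates a different, conditional one. In simulation at 140/35 the standardised risk difference hardly moves: 17.2 versus 17.1 points at a 35% share and 14.8 versus 14.8 at 50%. The standard error of the log odds ratio rises with the extra term (0.74 to 0.81, and 0.81 to 0.88). Power rises because the log odds ratio grows by more than its standard error.

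**Chance imbalance in CVD is not a second harm.** With 70 versus 35 patients the between-arm difference in CVD share has SD √[p(1-p)(1/70 + 1/35)], about 10 points for p between 0.35 and 0.50. That variation is already in the standard error and the simulated power. Protocol 5.3 is silent on stratification, which is weaker than saying there is none.

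**The size rests on unknowns.** A reader might take a gain above ten points from a favourable setting. A short run of 600 trials at 130/30 and a 50% share showed 55% to 68% Wald power; 1,500 trials gave 55% to 63%. Single Wald settings did reach 10-11 points (58.8% to 68.6% in the table; 41% to 52% at 140/35 with a 50% share). They are extremes at a share the documents do not report. At 140/35 the likelihood-ratio gain is about 1 point at a 10% share (81.7% to 82.6%).

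**The simulation suits the fix.** It draws percent change independently of baseline and CVD, which makes log(baseline/own target) the ideal covariate. That is fair, and a reason to treat the gains as indicative.

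**The other two goals partly cover this.** Each has one limit for everyone analysed, so baseline does its job there. True, but the own-target result will still be reported with its own odds ratio and p-value.

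**Conclusion.** The mismatch is real: the model was written for a fixed limit and is reused for a patient-specific one. The consequence is lost efficiency and a harder-to-read odds ratio in an exploratory analysis, not bias and not false positives.

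With the plan's effect and 70 versus 35 patients, adjusting for the target is worth about 1 to 4 points of power at a 10-20% CVD share and about 3 to 9 points at 35-50%. It gives a conditional odds ratio roughly 7-40% larger. If all patients shared one target there would be no gain. These sizes depend on the assumed baseline distribution and CVD share; the direction was the same in every setting tried.

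Severity: minor. It is worth doing because it costs almost nothing.

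**What to change.** For the own-target endpoint only, and before unblinding so that the covariate is not chosen from the results, use one of these:

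- Add CVD status (yes/no) as a factor: MODEL ANL01FL = TRT BASE CVD, with CVD in the CLASS statement. This adds one parameter.
- Replace BASE with log(baseline LDL-C / the patient's own target of 70 or 100 mg/dL). This adds no parameter.

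Name one as the planned model. Also state how cardiovascular disease is identified, since SAP 3.7.4 gives no definition and both the scoring and the covariate depend on it. Describe the result as an odds ratio conditional on target.

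The below-100 analysis (CVD patients excluded) and the below-70 analysis (one limit) need no change.

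The cost is a sentence of SAP text and a line of code. No new data are needed, because CVD status is already derived to score the endpoint.

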** ANL01FL = Reaching treatment goal, where 1=Yes 0=No          **
** TRT = Treatment group where 0 = placebo, 1= MGL-3196          **
** BASE = Baseline LDL-C                                         **
*****
PROC GENMOD DESCENDING;
  CLASS TRT;
  MODEL ANL01FL = TRT BASE / d=b link=logit;
  ESTIMATE "MGL3196 vs Placebo" TRT -1 1;
RUN;
```

It is observed that the screening values and baseline values of LDL-C have relatively high variation. Therefore, the change from screening to Week 12 LOCF in LDL-C will also be explored.

Due to the variation between screening and baseline values of LDL-C, it is expected that some patients will have baseline LDL-C <100 mg/dL. Therefore, more exploratory analysis of reaching LDL-C treatment goals at Week 12 based on patients with baseline LDL-C ≥100 mg/dL only may be conducted.

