10.2.4 Sample Size Determination

Up to 105 patients in total will be randomized to 1 of 2 treatments (70 patient to MGL-3196, 35 patients to placebo). It is estimated that the treatment difference of percent change in LDL-C from baseline to Week 12 between any dose of the MGL-3196 group and the placebo group is about -20%. With a common standard deviation for the change in LDL-C at 20%, 27 patients per group to complete the Week 12 visit will provide 90% power with a two-sample t-test. The significance level is set as 0.025 for the consideration of multiplicity in comparisons of 2 daily dosing regimens of MGL-3196 vs. placebo group. The enrollment size is designed to allow for dropouts before the 12-week visit, and as such, patients who drop out of the study will not be replaced.

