3. STATISTICAL METHODOLOGY

3.1 Baseline, Endpoint, and Other Statistical Considerations

Baseline for all efficacy and safety variables will be defined as Baseline visit (Day 1). If the measurement at this visit is missing, the last measurement prior to the first dose of randomized study drug will be used.

Only lipids measured less than 2 days after the last dose of study drug are considered as a valid post-baseline lipid assessment.

Post-baseline lipid assessments will be assigned a visit number based on the date of assessment relative to the first dose of the double-blind study drug. Visit windows will be defined as the scheduled time from dosing date with a 7-day window (± 7 days). Within a visit window, if a scheduled visit occurs, then the measurement from this scheduled visit will be used as the measurement for this visit window. If no scheduled visit occurs within a visit window, the last measurement within the window will be used. If no visits occur within a visit window, the measurement of this visit will be treated as missing.

Descriptive statistics (number of patients, mean, standard deviation, median, minimum, and maximum) will be used to summarize the continuous data. Discrete measures will be summarized using counts and percentages.

The summary and analysis of efficacy and safety data will be based on the MGL-3196 and placebo group. The primary efficacy and selected secondary endpoints will also be analyzed by MGL-3196 exposure level for the patients taking MGL-3196: higher exposure group and lower exposure group. The MGL-3196 exposure levels are determined by the plasma MGL-3196 concentration at Week 2 and later visits to represent the overall MGL-3196 exposure level for patients. That is, patients satisfies one of the following two conditions will be included in high exposure group: projected Week 2 AUC >5000 mg*h/L, or if Week 2 AUC <5000 but Week 4 predose >1.5 ng/mL (if on 60mg). Another analysis will be based on the [REDACTED] level for the patients taking MGL-3196: higher increase ($\geq 140\%$) and lower increase ($<140\%$) in [REDACTED] from baseline to Week 12.

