3.7.3 Subgroup Analysis of LDL-C

The subgroup analysis of LDL-C will be based on the mITT population. Since the analyses are for descriptive purposes only, no adjustments will be made for multiplicity.

The analysis of LDL-C will be performed based on MGL-3196 exposure group. In the analysis of LDL-C based on MGL-3196 exposure group, the patients who are taking MGL-3196 will be categorized into higher and lower exposure groups. The same ANOVA and ANCOVA models will be used, with pairwise comparisons between each exposure group versus placebo will be provided.

The analysis of LDL-C will also be performed based on SHBG group. In the analysis of LDL-C based on SHBG group, the patients who are taking MGL-3196 will be categorized into groups with higher increase or lower increase of SHBG from baseline to Week 12. Patients who are taking MGL-3196 but do not have Week 12 SHBG values will not be included. The same ANOVA and ANCOVA models will be used, with pairwise comparisons between each exposure group versus placebo to be provided.

The final dose of MGL-3196 (100 mg or 60 mg) will also be used to repeat the primary efficacy analysis. Similar to the exposure group, an analysis will be performed, but with the final dose of MGL-3196 to categorize patients who are taking MGL-3196.

The primary efficacy analysis of LDL-C will be repeated based on the following subgroups:

- Statin subgroup (80 mg Atorvastatin, 20/40 mg Rosuvastatin, or No/Low Dose Statin);
- Exposure group, SHBG group, in combination with statin subgroup;
- Gender subgroup (male, or female);
- Exposure group, SHBG group, in combination with gender subgroup;
- Baseline LDL-C value (<100 mg/dL, or \geq 100 mg/dL);
- Statin and baseline LDL-C subgroup;

- Exposure group, SHBG group, Final MGL-3196 dose group, in combination with baseline LDL-C subgroup;
- Baseline BMI value (<25 kg/m², or ≥25 kg/m²; and <30 kg/m², or ≥30 kg/m²);
- Exposure group, SHBG group, Final MGL-3196 dose group, in combination with baseline BMI subgroup;
- Average TSH between baseline and screening subgroup (<2 mIU/L, or ≥2 mIU/L);
- Exposure group, SHBG group, Final MGL-3196 dose group, in combination with average TSH between baseline and screening subgroup;

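### The primary LDL-C analysis adjusts for nothing; putting both Day 1 and screening LDL-C in the model would narrow the confidence interval at little cost

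*SAP*

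**What the plan says.** SAP 3.1 takes the Day 1 measurement as baseline. If it is missing, the last value before the first dose is used, which can be the screening value.

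SAP 3.7.2 analyses percent change in LDL-C at Week 12 with treatment as the only model term. Day 1 LDL-C is a covariate only in the additional analysis of absolute change. Protocol 10.2.1.1 had specified an analysis of covariance with baseline LDL-C for the primary analysis.

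SAP 3.7.4 states: "It is observed that the screening values and baseline values of LDL-C have relatively high variation". It expects some patients to be below 100 mg/dL at baseline, although inclusion criterion 5 requires at least 100 mg/dL. Its response is that "the change from screening to Week 12 LOCF in LDL-C will also be explored".

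A lipid panel is drawn at screening and again on Day 1 (Protocol 9.8), and the panel includes calculated LDL-C (Protocol Appendix B). No LDL-C analysis model uses both values. For TSH the SAP does combine the two visits, in a subgroup defined as "Average TSH between baseline and screening subgroup".

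**The concern.** Percent change from Day 1 carries the Day 1 error of each patient. A patient who happens to read high on Day 1 appears to improve, and one who reads low appears to worsen. This adds variance in both arms. Randomisation keeps the comparison unbiased, but the interval is wider than it need be.

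Two pre-randomisation values together help to separate a patient's usual level from the Day 1 error. Change from screening does not do this. It replaces the Day 1 error with the screening error, and if screening LDL-C decided eligibility it also brings in regression to the mean. At stake is precision in the primary estimate, not its validity.

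**Working it through.** **1. The plan's own figure.** SAP section 4 assumes a difference of 20 points, an SD of 20% and no covariate: "27 patients per group to complete the Week 12 visit will provide 90% power with a two-sample t-test" (Protocol 10.2.4, same in the SAP), and "The significance level is set as 0.025 for the consideration of multiplicity". With the noncentral t distribution and two-sided 0.025 (sidedness is not stated), 26 per group gives 89.8% power and 27 gives 91.0%. The figure is reproduced.

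**2. Model for the gain.** On the log scale:
- screening s = t + e_s
- Day 1 b = t + e_b
- Week 12 y = t + effect + r + e_y

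Here t has between-patient SD τ, each e has within-patient SD w, and r is variation in response. The outcome is D = y − b, with variance V = Var(r) + 2w², held at 0.20² = 0.04 to match the SAP. Neither τ nor w is in the documents. I assume τ = 30% and w from 5% to 14%.

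Since Cov(D, s) = 0 and Cov(D, b) = −w², the share of variance removed is:
- screening only: 0
- Day 1 only: w⁴ / [V(τ² + w²)]
- both: w²(τ² + w²) / [V(2τ² + w²)]

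Example, w = 10%:
- Day 1 only: 0.0001 / (0.04 × 0.10) = 2.5%
- both: 0.01 × 0.10 / (0.04 × 0.19) = 13.2%
- both over Day 1 only: 1 − 0.868/0.975 = 10.9%

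| w | Day 1 only | Both | Both over Day 1 only | Residual SD, both | Both, net of 2 df |
|---|---|---|---|---|---|
| 5% | 0.2% | 3.2% | 3.0% | 19.7 | 0.6% |
| 8% | 1.1% | 8.3% | 7.3% | 19.2 | 5.9% |
| 10% | 2.5% | 13.2% | 10.9% | 18.6 | 10.9% |
| 12% | 5.0% | 19.3% | 15.1% | 18.0 | 17.2% |
| 14% | 8.8% | 26.9% | 19.9% | 17.1 | 25.0% |

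The last column multiplies residual variance by 1 + 2/76 = 1.026, the expected cost of two covariates with 81 completers.

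**3. Effect of the entry cut-off.** The table ignores the 100 mg/dL criterion. I simulated 400,000 patients with τ = 30%, an assumed median LDL-C of 140 mg/dL and screening values kept only at 100 mg/dL or above. The total reduction at w = 14% stays at about 27%. The increment over Day 1 alone falls from about 20% to about 17%, because truncation makes Day 1 by itself more informative. I therefore take 3% to 17% as the increment.

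**4. What it buys.**
- *Planning comparison, 27 against 27, 0.025:* power is 91.0% with no covariate and 90.4% with screening alone. With both it runs from 90.8% (w = 5%) to 96.9% (w = 14%), and the number needed per group runs from 27 down to 21. At w = 5% the gain does not repay the two degrees of freedom.
- *The SAP's primary comparison, all MGL-3196 against placebo:* assume 54 against 27 completers and two-sided 0.05. Power is 98.7% with no covariate and 98.8% to 99.8% with both. The 95% half-width is 1.99 × 20 × √(1/54 + 1/27) = 9.4 points. With residual SD 19.7 to 17.1 it is 9.2 to 8.0 points. Multiplying by √1.026 for the two covariates gives 9.4 to 8.1.

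**The case against.** The case against is that this is an optional efficiency gain of unknown size. Much of that stands.

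- **The size cannot be derived from the documents.** They call the variation high and give no SD or correlation. Any narrow figure rests on assumed within-patient error and response variation, so only the range is defensible.
- **Adjusting for Day 1 is a separate matter.** The protocol already specified it and the SAP dropped it. Only the increment over Day 1 belongs to screening. In this model, however, Day 1 alone recovers just 0.2% to 8.8%, so restoring the protocol's model is not enough.
- **Screening is an imperfect covariate.** It may precede the move to evening statin dosing (Protocol 6.2), and it has no ultracentrifugation value. Both can weaken its correlation with Day 1 and shrink the gain. Neither can bias the randomised comparison.
- **The TSH precedent is weak.** That average only defines a subgroup.

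A reader might infer more than the documents support:
- *That the SAP ignores screening LDL-C.* It does not: there is the exploratory analysis and the fallback rule.
- *That adding screening to the existing model would help.* It would not: with no Day 1 term the reduction is 0%.
- *That the change is free.* It costs two degrees of freedom and needs an extra rule.
- *That the primary comparison is biased or underpowered.* Neither follows.
- *That the change-from-screening analysis should go.* It asks whether the result depends on the choice of baseline, which is a different question from precision, and it is labelled exploratory.

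**Conclusion.** The point holds as a minor improvement in precision. The SAP identifies a noisy baseline, holds two pre-randomisation values, and uses neither as a covariate in its primary model. Including both would cut residual variance by about 3% to 27% against the SAP's model and about 3% to 17% against Day 1 adjustment alone, before the two degrees of freedom. This rests on the planning SD of 20%, assumed between-patient SD 30% and within-patient SD 5% to 14%, and, for the 17%, screening truncated at 100 mg/dL. At the bottom of the range the net gain is negligible. The SAP's description of the variation as relatively high suggests a value above that, but does not establish one.

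The assurance against bias applies to the randomised comparison of all MGL-3196 with placebo. The comparisons by final dose may also gain precision, but those groups are formed by Week 2 drug level, and covariate adjustment does not make them randomised.

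**What to change.** Before unblinding, amend SAP 3.7.2 as follows.

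1. Keep percent change from Day 1 to Week 12 as the endpoint.
2. Make the primary model an analysis of covariance with treatment, Day 1 LDL-C and screening LDL-C. Use the calculated LDL-C for both covariates, since screening has no ultracentrifugation value.
3. Add a rule for patients whose missing Day 1 value is replaced by the screening value, because their two covariates are then identical. One option is to keep the substituted value in both terms and repeat the analysis without those patients.
4. Report the screening-to-Day 1 correlation and the SD of the log difference from blinded data. In the model above that SD equals w√2, so 7% corresponds to w = 5% and 20% to w = 14%. This shows which row of the table applies.
5. Leave the change-from-screening analysis as exploratory.

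The cost is two terms in the model statement, two degrees of freedom (about 2.6% of variance with 81 completers) and one data-handling rule. No new data are needed.
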